6.1.1 Definitions

6.1.1.1 Adverse Event

An adverse event (AE) is defined as any untoward medical occurrence in a subject or clinical investigation subject administered a pharmaceutical product and which does not necessarily have a causal relationship with this treatment. An adverse event can therefore be any unfavorable and unintended sign (including an abnormal laboratory finding), symptom, or disease temporally associated with the use of a medicinal (investigational) product, whether or not the event is considered causally related to the use of the product.

Such an event can result from use of the drug as stipulated in the protocol or labeling, as well as from accidental or intentional overdose, drug abuse, or drug withdrawal. Any worsening of a pre-existing condition or illness is considered an adverse event.

Worsening in severity of a reported adverse event should be reported as a new adverse event. Laboratory abnormalities and changes in vital signs are considered to be adverse events only if they result in discontinuation from the study, necessitate therapeutic medical intervention, meets protocol specific criteria (see Section 6.1.9 Toxicity Management) or if the investigator considers them to be adverse events.

For this protocol, disease progression is an efficacy endpoint. These data will be captured as efficacy assessment data only. Thus, events that are clearly consistent with the expected pattern of progression of the underlying disease (such as transformation to more aggressive histology) will result in discontinuation from the study and should not be recorded as adverse events but reported on the Study Completion eCRF. However, if a subject experiences an adverse event (e.g., pneumonia, pyrexia, fatigue, etc.) and is also found to have disease progression, report the adverse event. If there is any uncertainty as to whether an event is due to disease progression, it should be reported as an adverse event.

An elective surgery/procedure scheduled to occur during a study will not be considered an adverse event if the surgery/procedure is being performed for a pre-existing condition and the surgery/procedure has been pre-planned prior to study entry. However, if the

pre-existing condition deteriorates unexpectedly during the study (e.g., surgery performed earlier than planned), then the deterioration of the condition for which the elective surgery/procedure is being done, will be considered an adverse event.

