Hospitalization of a subject to allow observation and management (e.g., for intravenous (IV) hydration) for the purpose of TLS prophylaxis will not be captured as an SAE, unless there is an additional reason for hospitalization or an additional criterion for seriousness other than hospitalization (e.g., abnormal post-dose TLS laboratories that necessitate therapeutic medical intervention, etc.).

Hospitalization of a subject following the 30 Day Safety Follow-Up visit due to a subsequent line of therapy will not be captured as a SAE.

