6.1.9.2 Dose Modifications Based on Toxicities

Dosing interruption and/or dose reduction may be required. See [Table 7](#) for dose modifications for hematologic and other toxicities related to venetoclax. For subjects who have had a dosing interruption greater than 1 week during the first 5 weeks of dose titration or greater than 2 weeks when at the daily dose of 400 mg, TLS risk should be reassessed to determine if restarting at a reduced dose is necessary (e.g., all or some levels of the dose titration).

Tumor Lysis Syndrome

If a subject experiences blood chemistry changes suggestive of TLS, the following day's venetoclax dose should be withheld. If resolved within 24 to 48 hours of last dose, treatment with venetoclax can be resumed at the same dose. For events of clinical TLS or blood chemistry changes requiring more than 48 hours to resolve, treatment should be resumed at a reduced dose ([Table 7](#) and [Table 8](#)). When resuming treatment with venetoclax after interruption due to TLS, the instructions for Prophylaxis for tumor lysis syndrome should be followed.

Other Toxicities

Treatment with venetoclax should be withheld for any grade 3 or 4 non-haematological, grade 3 or 4 neutropenia with infection or fever, or grade 4 haematological toxicities, except lymphopenia. To reduce the risk of infection associated with neutropenia, granulocyte-colony stimulating factor (G-CSF) may be administered with venetoclax if clinically indicated. Once the toxicity has resolved to grade 1 or baseline level (recovery), therapy with venetoclax may be restarted at the same dose. If the toxicity recurs, and for any subsequent occurrences, the dose reduction guidelines in [Table 7](#) and [Table 8](#) should be followed when resuming treatment with venetoclax following resolution. A larger dose reduction may occur at the discretion of the investigator. For subjects who require dose reductions to less than 100 mg for more than 2 weeks, due to adverse events, discontinuation of venetoclax should be considered.

Table 7. Recommended Dose Modifications for Toxicities

Event	Occurrence	Action
Tumor Lysis Syndrome		
Blood chemistry changes or symptoms suggestive of TLS	Any	Withhold the next day's dose. If resolved within 24 – 48 hours of last dose, resume at the same dose.
		For any blood chemistry changes requiring more than 48 hours to resolve, resume at a reduced dose (Table 8)

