Appendix F. Definitions of Laboratory and Clinical Tumor Lysis Syndrome

Metabolic Abnormality	Criteria for Classification of Laboratory Tumor Lysis Syndrome	Criteria for Classification of Clinical Tumor Lysis Syndrome
Hyperruricemia	Uric acid > 8.0 mg/dL (475.8 µmol/liter) in adults or above the upper limit of the normal range for age in children	
Hyperphosphatemia	Phosphorus > 4.5 mg/dL (1.5 mmol/liter) in adults or > 6.5 mg/dL (2.1 mmol/liter) in children	
Hyperkalemia	Potassium > 6.0 mmol/liter	Cardiac dysrhythmia or sudden death probably or definitely caused by hyperkalemia
Hypocalcemia	Corrected calcium < 7.0 mg/dL (1.75 mmol/liter) or ionized calcium < 1.12 (0.3 mmol/liter) [†]	Cardiac dysrhythmia, sudden death, seizure, neuromuscular irritability (tetany, paresthesias, muscle twitching, carpopedal spasm, Trousseau's sign, Chvostek's sign, laryngospasm, or bronchospasm), hypotension, or heart failure probably or definitely caused by hypocalcemia
Acute kidney injury [‡]	Not applicable	Increase in the serum creatinine level of 0.3 mg/dL (26.5 µmol/liter) (or a single value > 1.5 times the upper limit of the age-appropriate normal range if no baseline creatinine measurement is available) or the presence of oliguria, defined as an average urine output < 0.5 mL/kg/hr for 6 hrs

[†] The corrected calcium level in milligrams per deciliter = measured calcium level in milligrams per deciliter + 0.8 × (4-albumin in grams per deciliter).

[‡] Acute kidney injury is defined as an increase in the creatinine level of at least 0.3 mg per deciliter (26.5 µmol per liter) or a period of oliguria lasting 6 hours or more. By definition, if acute kidney injury is present, the subject has clinical tumor lysis syndrome. Data about acute kidney injury from Levin et al.

Note: In laboratory tumor lysis syndrome, two or more metabolic abnormalities must be present during the same 24-hour period within 3 days before the start of therapy or up to 7 afterward. Clinical tumor lysis syndrome requires the presence of laboratory tumor lysis syndrome plus an increased creatinine level, seizures, cardiac dysrhythmia, or death.

Appendix G. Recommendations for Initial Management of Electrolyte Abnormalities and Prevention of Tumor Lysis Syndrome (TLS)

Section 1: First Dose of Venetoclax or Dose Escalation

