- Within the first 24 hours after either the first dose or dose escalation, if any laboratory criteria below are met, the subject should be hospitalized for monitoring and the investigator notified. No additional venetoclax doses should be administered until resolution. Rapidly rising serum potassium is a medical emergency.
- Nephrology (or other acute dialysis service) should be contacted/consulted (per institutional standards to ensure emergency dialysis is available) on admission for any subject hospitalized prophylactically or in response to laboratory changes.
- IV fluids (e.g., D5 1/2 normal saline) should be initiated at a rate of at least 1 mL/kg/hr rounded to the nearest 10 mL (target 150 to 200 mL/hr; not < 50 mL/hr). Modification of fluid rate should also be considered for individuals with specific medical needs.
- Monitor for symptoms or signs of TLS (e.g., fever, chills, tachycardia, nausea, vomiting, diarrhea, diaphoresis, hypotension, muscle aches, weakness, paresthesias, mental status changes, confusion and seizures). If any clinical features are observed, recheck potassium, phosphorus, uric acid, calcium and creatinine within 1 hour STAT.
- Vital signs should be taken at time of all blood draws or any intervention.
- The management recommendations below focus on the minimum initial responses required. If a diagnosis of TLS is established, ongoing intensive monitoring and multi-disciplinary management will be per institutional protocols.

In addition to the recommendations in the table below, for subjects receiving the first dose of venetoclax.

- For potassium increase ≥ 0.5 mmol/L from baseline, or any value > 5.0 mmol/L, recheck potassium, phosphorus, uric acid, calcium and creatinine within 1 hour STAT and follow first guideline.
- For phosphorus increase of > 0.5 mg/dL AND > 4.5 mg/dL, administer phosphate binder and recheck potassium, phosphorus, uric acid, calcium and creatinine within 1 hour STAT.

Abnormality	Management Recommendations
Hyperkalemia (Including Rapidly Rising Potassium)	

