Calcium \leq 7.0 mg/dL (1.75 mmol/L)	
 • Administer calcium gluconate 50 to 100 mg/kg IV slowly with ECG monitoring. • Telemetry. • Recheck potassium, phosphorus, uric acid, calcium and creatinine in 1 hr STAT. 
 ○ If calcium normalized 1 hour later, repeat potassium, phosphorus, uric acid, calcium and creatinine 2 and 4 hrs., later, if no other evidence of tumor lysis. • Calculate corrected calcium and check ionized calcium if albumin low.

AND
 
Subject symptomatic (e.g., muscle cramps, hypotension, tetany, cardiac arrhythmias)
	
Hyperphosphatemia	
Phosphorus \geq 5.0 mg/dL (1.615 mmol/L) with \geq 0.5 mg/dL (0.16 mmol/L) increase	
 • Administer a phosphate binder (e.g., aluminum hydroxide, calcium carbonate, sevelamer hydroxide, or lanthanum carbonate). • Nephrology (or other acute dialysis service) notification (dialysis required for phosphorus \geq 10 mg/dL). • Recheck potassium, phosphorus, uric acid, calcium and creatinine in 1 hr STAT. 
 ○ If phosphorus $<$ 5.0 mg/dL 1 hour later, repeat potassium, phosphorus, uric acid, calcium and creatinine 2 and 4 hrs., later, if no other evidence of tumor lysis.
Creatinine	
Increase \geq 25% from baseline	
 • Start or increase rate of IV fluids. • Recheck potassium, phosphorus, uric acid, calcium and creatinine in 1 to 2 hours STAT.

* Check rasburicase label for contraindications.

Section 2: Ongoing Dosing of Venetoclax

Management of electrolyte changes from last value at intervals $>$ 24 hours after either the first dose or dose escalation (e.g., 48 or 72 hours) are as below.

Note: If the subject is hospitalized, no additional venetoclax doses should be administered until resolution.

- For potassium, admit subject for any increase ≥ 1.0 mmol/L (1.0 mEq/L), or any level $>$ upper limit of normal.
 - Refer to the management guidelines for electrolyte changes observed within the first 24 hours after either the first dose or dose escalation (see prior table).
- If a smaller potassium increase is observed that does not meet the criteria for admission above, recheck potassium, phosphorus, uric acid, calcium and creatinine in 24 hours and confirm no evidence of tumor lysis prior to further venetoclax dosing.

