- For uric acid, calcium, phosphorus and creatinine, refer to the management guidelines for electrolyte changes observed within the first 24 hours after either the first dose or dose escalation (see prior table).

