Tumor Lysis Syndrome (three searches)	
 1) SMQ – "Tumour lysis syndrome" (Narrow-scope) 2) SMQ – "Tumour lysis syndrome" (Narrow) plus PT terms of "Hyperkalaemia," "Hyperuricaemia," "Hyperphosphataemia," "Hypocalaemia," "Blood potassium increased," "Blood uric acid increased," "Blood phosphorus increased," "Blood calcium decreased" 3) SMQ – "Tumour lysis syndrome" (Narrow) plus broad-scope terms with algorithm applied (ie., two events from category B and one event from category C required for a subject to be counted as having a TLS event)
Neutropenia	PT terms – "Neutropenia," "Neutrophil count decreased," "Febrile neutropenia," "Agranulocytosis," "Neutropenic infection," and "Neutropenic sepsis"
Serious Infection, Including Opportunistic Infections	SAEs in the SOC of "Infections and Infestations"
Second Primary Malignancy	SMQ – "Malignant tumours" (Narrow) and "Myelodysplastic syndromes" (Narrow)
Lymphopenia	PT terms – "Lymphopenia" and "Lymphocyte count decreased"
Anemia	PT terms – "Anaemia" and "Haemoglobin decreased"
Thrombocytopenia	PT terms – "Thrombocytopenia" and "Platelet count decreased"
Drug Induced Liver Injury (DILI)	SMQ – "Drug related hepatic disorders – comprehensive search"
Medication Error	SMQ – "Medication error" (broad)

SMQ = Standardised MedDRA Query;

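### No planned output gives the TLS rate on the protocol's own laboratory definition, because the SAP counts TLS only from coded adverse event terms

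*SAP*

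**What the plan says.** **Definition.** The note to protocol Appendix F requires for laboratory TLS that "two or more metabolic abnormalities must be present during the same 24-hour period within 3 days before the start of therapy" or in the 7 days after it. The limits are uric acid above 8.0 mg/dL, phosphorus above 4.5 mg/dL, potassium above 6.0 mmol/L, and corrected calcium below 7.0 mg/dL (or low ionized calcium). Clinical TLS is laboratory TLS plus raised creatinine, seizure, dysrhythmia or death. Protocol 6.1.1.4 names TLS as one of two AEs of special interest.

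**AE analysis.** SAP 11.2, Table 3, gives three searches:

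1. the narrow standardised MedDRA query (SMQ) for TLS;
2. that query plus eight single electrolyte or uric acid preferred terms;
3. that query plus broad-scope terms under an algorithm, with "two events from category B and one event from category C required for a subject to be counted as having a TLS event".

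Each is reported as the number of subjects with at least one treatment-emergent AE, with a listing of those AEs.

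**Laboratory analysis.** SAP 11.3 and 11.3.1 plan mean changes by visit, CTCAE shift tables for each variable at maximum and final grade, and grade 3–4 listings. The one rule joining analytes in time is potential drug-induced liver injury (DILI): raised ALT or AST with raised bilirubin within 72 hours.

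**The concern.** TLS is the reason for the five-week titration, the prophylaxis and the timed blood draws. The protocol carries a value-based definition, and the values it needs are collected: protocol Table 4 includes all four analytes plus albumin and creatinine, and protocol 5.3.1.1 has sites enter local results in the eCRF. The report would nevertheless show only how often sites wrote certain terms. The background in protocol section 3.0 describes earlier venetoclax experience in terms of clinical and laboratory TLS; this trial would have no rate on its own laboratory definition to set beside it. The SAP gives DILI both a term search and a laboratory rule, but gives TLS only term searches, although DILI is not among the AEs of special interest named in the protocol.

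**Working it through.** The plan states no expected TLS rate, so there is no figure to reproduce. The check sets the definition against each planned output.

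**Step 1. What each output uses.**

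| Output | Input | Two limits together? | Period |
|---|---|---|---|
| Appendix F laboratory TLS | measured values | yes, same 24 h | 3 days before to 7 days after start |
| Search 1 | coded AE terms | no | first dose to 30 days after last dose |
| Search 2 | coded AE terms, one is enough | no | same |
| Search 3 | coded AE terms, category rule | no laboratory limits | same |
| Shift tables | CTCAE grade, one analyte at a time | no | maximum and final, to 30 days after last dose |
| Grade 3–4 listings | values | not tested, not counted | any time |

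The maximum grade of one analyte and the maximum of another may fall on different days. Shift tables therefore cannot show two abnormalities in one 24-hour period.

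**Step 2. Three illustrative subjects.** Assume that an AE recorded as TLS falls under the narrow query. Protocol 6.1 lets the site record a diagnosis if known, or otherwise a sign or symptom.

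| Subject | Appendix F | Search 1 | Search 2 | Search 3 |
|---|---|---|---|---|
| A: potassium and uric acid over their limits on one early panel, recorded as TLS | yes | yes | yes | yes |
| B: same panel, recorded as hyperkalaemia and hyperuricaemia | yes | no | yes | only if category B and C terms are present |
| C: one isolated hyperkalaemia AE at Week 40 | no | no | yes | no |

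Search 1 loses B. Search 2 counts B and C alike. Search 3 depends on other terms being reported; the documents do not list the category members. The mismatch can also go the other way: a site may record TLS when two limits were not met within 24 hours, or outside the Appendix F window.

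**Step 3. Do qualifying cases reach the AE data at all?** Mostly they should.

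- Protocol 5.3.1.1, 6.1.9.1 and Appendix D note j tell sites to correct electrolyte abnormalities promptly after the 6–8 h and 24 h panels, with no symptom condition.
- Under protocol 6.1.1.1, laboratory abnormalities are AEs when they "necessitate therapeutic medical intervention, meets protocol specific criteria (see Section 6.1.9 Toxicity Management) or if the investigator considers them to be adverse events".
- Protocol 6.1.1.2 lifts the exemption for prophylactic admissions when there are "abnormal post-dose TLS laboratories that necessitate therapeutic medical intervention".
- Protocol 6.1.9.2 adds: "If a subject experiences blood chemistry changes suggestive of TLS, the following day's venetoclax dose should be withheld".

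What stays open is the term under which a case is recorded, as in step 2.

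**Step 4. Precision of the added rate.** With x of n = 200 dosed subjects qualifying, the Clopper–Pearson limits are the 0.025 quantile of Beta(x, n − x + 1) and the 0.975 quantile of Beta(x + 1, n − x). For x = 0 the upper limit is 1 − 0.025^(1/200) = 1.83%. The values of x are assumptions.

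| x | Rate | Exact 95% CI |
|---|---|---|
| 0 | 0% | 0–1.8% |
| 2 | 1.0% | 0.1–3.6% |
| 10 | 5.0% | 2.4–9.0% |

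**The case against.** The strongest reply is that nothing promised is missing. Protocol 8.1.4 and its subsections plan AE summaries, grade shifts and grade 3–4 listings, and the SAP delivers them. The protocol names TLS as an adverse event, so finding it by AE search follows the protocol, and Appendix F is not made an endpoint anywhere. The three searches run from narrow to broad and are shown by preferred term with listings, so a reader could partly rebuild cases by hand. All of this stands. It makes the point an improvement and not a breach, but a partial hand reconstruction is still not a count.

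A reader might infer that some cases escape recording altogether, notably low calcium with high phosphorus. Appendix G treats low calcium only with "Subject symptomatic (e.g., muscle cramps, hypotension, tetany, cardiac arrhythmias") and, for phosphorus, asks for a rise as well as a high level. The documents do not support that inference. Appendix G is not the only instruction: the correct-promptly rule in step 3 has no symptom condition, and a corrected value is an AE. Nor do the blood-draw schedule and its gaps show that any case was missed.

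The reply also has force against the remedy. The Appendix F window ends 7 days after the first dose, which is Day 8, the day of the 50 mg step, so it covers essentially the 20 mg week. Protocol 6.1.9.1 places TLS risk at each dose increase. The documents do not say that draw times are entered in the eCRF. These points limit what the added table can show; they do not remove its use.

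**Conclusion.** The point holds as a cheap improvement, between optional and recommended. No planned output counts subjects meeting Appendix F laboratory TLS or the clinical TLS that depends on it, and none of the three AE searches yields that rate. The size and direction of the difference between the searches and the Appendix F rate cannot be determined from the documents. The conclusion rests on the text of SAP 11.2 to 11.3.1 and on the values being in the eCRF as protocol 5.3.1.1 states; no assumption about under-reporting is needed. The consequence is confined to how TLS is described in a descriptive single-arm trial.

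**What to change.** Add to SAP 11.3.1, beside the DILI rule:

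- **Laboratory TLS:** per subject, two or more Appendix F limits for uric acid, phosphorus, potassium and albumin-corrected calcium within the same 24 hours, from the first dose through 7 days after it. If draw times are missing, use the same or consecutive calendar day. That is looser, since draws on consecutive days can be almost 48 hours apart, so flag subjects who qualify only this way.
- **Before dosing:** show separately the subjects already meeting the rule in the 3 days before the first dose.
- **Clinical TLS:** laboratory TLS plus an Appendix F clinical criterion, with creatinine from laboratory data and seizure, dysrhythmia or death from AE data.
- **Reporting:** number, percentage and exact 95% CI for each, cross-tabulated with the three AE searches. Keep those searches and their listings.
- **Later dose steps:** optional and labelled exploratory, because Appendix F does not define them.

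The cost is one SAP paragraph, one derivation and one table, with no new samples. The limits to state with it are:

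- the window supplements the AE searches and cannot replace them;
- uric acid may read falsely low after rasburicase (protocol Table 4, note b);
- ionized calcium is not in Table 4;
- draw times may be incomplete.

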Appendix H. Adverse Events Commonly Associated with CLL Study Population and/or Progression of CLL

Disease-Related Events – CLL

Lymphadenopathy
Splenomegaly
Hepatomegaly
Leukemia cutis (macules, papules, plaques, nodules, ulcers, or blisters)
Lymphocytosis
Cytopenias (neutropenia, anemia and thrombocytopenia)
Febrile neutropenia
Autoimmune hemolytic anemia
Autoimmune thrombocytopenia
Hypogammaglobulinemia
Infections (bacterial, viral, and fungal)
Second primary cancers, all types
Fatigue
Unexplained weight loss
Pyrexia
Bruising
Minor hemorrhages
Pain, all types
Malignant neoplasm progression, including death

Population-Related Comorbidities

Hypertension
Rheumatoid arthritis/osteoarthritis
Hyperlipidemia
Peptic ulcer
Inflammatory bowel disease
Coronary artery disease
Peripheral vascular disease

Cardiomyopathy

Valvular disease

Atrial fibrillation

Diabetes mellitus

Chronic obstructive pulmonary disease

Cerebrovascular accident

Transient ischemia attack

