The number and percentage of subjects with treatment-emergent adverse events will be tabulated by primary MedDRA System Organ Class (SOC) and preferred term (PT). The system organ classes will be presented in alphabetical order, and the preferred terms will be presented in alphabetical order within each system organ class.

Adverse Event

An overview of AEs will be presented consisting of the number and percentage of subjects experiencing at least one event for each of the following AE categories:

- Any treatment-emergent adverse event;
- Any treatment-emergent adverse event with reasonable possibility related to venetoclax by the investigator;
- Any treatment-emergent NCI toxicity (CTCAE V4.0) grade 3, or 4 adverse events;
- Any treatment-emergent NCI toxicity (CTCAE V4.0) grade 3, 4, or 5 adverse events;
- Adverse events broken down by NCI toxicity grade (Severity);
- Any treatment-emergent serious adverse event;
- Any treatment-emergent adverse event leading to discontinuation of venetoclax;

- Any treatment-emergent adverse event leading to venetoclax interruption;
- Any treatment-emergent adverse event leading to venetoclax dose reduction;
- Any treatment-emergent adverse event leading to death;
- Deaths.

The deaths in the overview summary include all deaths that occurring while the subject is still receiving venetoclax in this study and occurring off treatment within 30 days after the last dose of venetoclax.

For summary tables of AE by PT, subjects reporting more than one AE for a given PT will be counted only once for that term (most severe/highest grade incident for the severity tables and most related incident for the relationship tables). Subjects reporting more than one AE within an SOC will be counted only once for that SOC. Subjects reporting more than one AE will be counted only once in the overall total.

Adverse Events of Special Interest

Adverse events of special interest will be summarized. The list of adverse events of special interest is shown in [Table 3](#).

For each of the adverse event of interest, the number and percentage of subjects experiencing at least one treatment-emergent adverse event will be presented overall and by SOC and PT. In addition, a listing of treatment-emergent adverse events for subjects meeting each of the search criteria will be provided.

Table 3. Adverse Events of Special Interest

Risk	Search Criteria

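### The second-primary-malignancy search in SAP Table 3 does not exclude the study disease, so CLL events recorded as adverse events can be counted as second cancers

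*SAP*

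**What the plan says.** SAP Section 11.2 restricts the adverse-event summaries to treatment-emergent events and refers to Table 3 for the searches that define each event of special interest. The second-primary-malignancy row is "Malignant tumours' (Narrow) and 'Myelodysplastic syndromes' (Narrow") and nothing more. Neither the row nor the surrounding text removes terms for the disease under study. For each event of special interest, "the number and percentage of subjects experiencing at least one treatment-emergent adverse event will be presented overall and by SOC and PT", together with a listing of the events found.

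The protocol decides what reaches the adverse-event data. Section 6.1.1.1 sends events that clearly fit progression to the Study Completion form, giving transformation to a more aggressive histology as its example. It then adds: "If there is any uncertainty as to whether an event is due to disease progression, it should be reported as an adverse event". Appendix H, the list of events commonly associated with CLL or its progression, includes "Malignant neoplasm progression, including death". Second primary cancers have their own line in that list.

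The second tumor lysis search in Table 3 adds eight preferred terms to the narrow query. One run of them reads "Hyperphosphataemia,' 'Hypocalaemia,' 'Blood potassium increased".

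**The concern.** Every subject enters with a malignancy. A search built from a query for malignant tumours, with no carve-out for that malignancy, cannot by itself separate a new cancer from an uncertain or partly attributed CLL event. The protocol treats these as two concepts; the SAP search treats them as one.

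The number and percentage from this row will be read as the second-cancer frequency on venetoclax. SAP Section 3.0 says the plan is meant to guide the programming, so an exclusion that is not written may not be programmed. If stray CLL terms appear, someone must decide after seeing the data, in an open-label single-arm study, which of them to remove. A rule written beforehand avoids that.

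The spelling point is smaller. *Hypocalaemia* is not the "Hypocalcemia" of protocol Appendix F, where low calcium is a laboratory criterion for tumor lysis syndrome.

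**Working it through.** The plan states no expected count for either search, so there is no figure to reproduce. The check compares the texts and then bounds the effect.

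**Step 1. Which study-disease events can reach the search?**

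| Event | Protocol section | Destination |
|---|---|---|
| Clearly consistent with progression, including transformation | 6.1.1.1 | Study Completion form; not an adverse event |
| Serious or fatal, unequivocally due to progression | 6.1.1.3 | Not an adverse event |
| Death attributed solely to CLL progression | 6.1.3.1 | Study Completion form only |
| Any doubt whether progression is the cause | 6.1.1.1 | Adverse-event data |
| Serious event of a kind listed in Appendix H, not unequivocally progression | 6.1.1.3 | Reported to the sponsor as serious |
| Any other on-study death | 6.1.3.1 | Adverse-event form |

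The first three rows close the route; the last three leave it open. An event that takes an open route, is treatment-emergent and is coded to a term inside the query is counted, because Table 3 has no further filter.

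**Step 2. How large could the excess be?**

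Let *k* be the number of subjects whose only hit is a study-disease event recorded as treatment-emergent. The reported rate is then too high by *k*/200. The denominator is the 200 subjects planned to be dosed (SAP Section 4.3); the safety population is all who take at least one dose (SAP Section 5.1.1). The documents do not give *k*. The rates below are assumptions:

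- 0%: *k* = 0, excess 0 percentage points
- 1%: *k* = 0.01 × 200 = 2, excess 2/200 = 1 point
- 3%: *k* = 0.03 × 200 = 6, excess 6/200 = 3 points
- 6%: *k* = 0.06 × 200 = 12, excess 12/200 = 6 points

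**Step 3. The tumor lysis term.**

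Search 2 lists four conditions and then four laboratory terms in the same order: potassium, uric acid, phosphorus, calcium. The last two laboratory terms are "Blood phosphorus increased,' 'Blood calcium decreased", so the fourth condition is evidently low calcium. A case-insensitive exact match against the eight printed terms gave:

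- *Hypocalcaemia*: no match
- *Hypocalcemia*: no match
- *Blood calcium decreased*: match
- *Hyperkalaemia* (control): match

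Under literal matching, search 2 misses a subject only if the event is coded to hypocalcaemia and the subject has neither another listed term nor a narrow-query hit. Search 1 uses the narrow query alone. Search 3 uses the narrow query "plus broad-scope terms with algorithm applied". Neither depends on the typed list.

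**The case against.** The best defence is that most of the exclusion is made upstream. The protocol keeps clear progression out of the adverse-event data, and transformation is its own example of what stays out. Sections 6.1.1.2, 6.1.1.3 and 6.1.3.1 repeat the principle for serious events and deaths. Appendix H is a list of events treated as expected for reporting; it does not show that progression will be recorded. Any stray term would also appear by name in the preferred-term table and the listing. All of this stands, and it makes the risk conditional. It does not remove it: the exemptions cover clear, unequivocal or sole attribution, and a listing shows a misplaced event without taking it out of the count.

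The content of the MedDRA query is not in the documents either. That it captures CLL or progression terms is inferred from its name.

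Three stronger readings are tempting, and the documents do not support them:

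- A reader might infer that the malignancy count is certain to be wrong. It is not, because the excess is zero if the routing works fully.
- A reader might seek a relative inflation of the second-cancer rate, borrowing the 5.9% for serious malignant neoplasm progression shown in protocol Appendix I. That figure is in deleted text and describes other monotherapy studies. The documents give no expected second-cancer rate to divide by.
- A reader might fear that *Hypocalaemia* will be read as hypokalaemia. Hypocalcaemia is equally one letter away, and the pairing in the list shows what was meant. A programmer would probably catch the slip, and a text-extraction error cannot be fully excluded.

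**Conclusion.** The point holds in a limited form. As written, the second-primary-malignancy search can count a CLL event as a second cancer, because it has no study-disease exclusion and the protocol leaves a route for uncertain or partly attributed cases. This rests on two assumptions that the documents cannot settle: that such events are recorded, and that the query contains the terms to which they would be coded. The effect is therefore bounded by assumption only, at 0 to 6 percentage points, and zero is a possible outcome.

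The misspelled calcium term is a minor correction and does not carry the point. Nothing here shows a need to exclude recurrence of earlier cancers as well; that would require its own argument.

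**What to change.** In the second-primary-malignancy row of SAP Table 3, add: *excluding terms for CLL/SLL, its progression and Richter's transformation*. Produce the accompanying listing before the exclusion is applied, with excluded events flagged, so that a reader can check each one.

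In tumor lysis search 2 of the same table, change *Hypocalaemia* to *Hypocalcaemia*.

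The cost is one clause and one letter in a single table, plus a flag in one listing. No new data are needed.
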